**The following Amendments have been incorporated into this Integrated Protocol.**

AMENDMENT NUMBER	VERSION NUMBER	DATE
Amendment 5	1.0	10-June-2009
Amendment 6	1.0	22-March-2010
Amendment 8	1.0	15-Feb-2011
Amendment 11	1.0	13-Dec-2012

## Glossary and Abbreviations

6MWD	6-minute walking distance
AE	adverse event or experience
ALT	alanine aminotransferase (also known as SGPT, qv )
ALP	alkaline phosphatase
AST	aspartate aminotransferase (also known as SGOT, qv )
CCW	concalc for Windows
cGMP	cyclic guanosine monophosphate
CHE	Cholinesterase
CK	creatine kinase
CRF	case report form
eCRF	electronic case report form
CT	computed tomography
CTEPH	chronic thromboembolic pulmonary hypertension
CYP3A4	cytochrome P450 isoenzyme 3A4 (etc)
d	Day
EC	ethical committee
ECG	Electrocardiogram
eg	exempli gratia , for example
EQ-5D	EuroQol questionnaire
g	standard acceleration due to gravity at the Earth's surface, by definition: $g = 9.80665 \text{ m/sec}^2$
GCP	Good Clinical Practice
GGT	gamma glutamyl transpeptidase
GLDH	glutamate dehydrogenase
h	Hour
H	Height
HDPE	High Density Polyethylen
HEOR	Health Economics, Outcomes and Reimbursement
HPLC	high pressure liquid chromatography
ie	id est , that is
IR	immediate release
INR	international normalized ratio (prothrombin time expressed in relation to normal value)
IRB	Institutional Review Board
iv	Intravenous
IVR / IVRS	interactive voice response system
LPH	Living with Pulmonary Hypertension questionnaire
M-1	metabolite M-1
mg	Milligram
mmHg	millimeter of mercury
MRR	Medical Research Report
NO	Nitric oxide
NT-proBNP	N-terminal pro-brain natriuretic peptide
O 2	Oxygen

PaCO 2	arterial partial pressure of carbon dioxide
PaO 2	arterial partial oxygen pressure
PEA	Pulmonary endarterectomy
PDE5	phosphodiesterase type-5
PH	pulmonary hypertension
PK	Pharmacokinetic
PTT	partial thromboplastin time
PvO 2	venous oxygen pressure
PVOD	Pulmonary-veno-occlusive disease
QC	quality control
SAE	serious adverse event
SaO 2	oxygen saturation
SAS	Statistical Analysis System
SBP	systolic blood pressure
tid	ter in die (3 times a day)
WHO	World Health Organization

## 1. INTRODUCTION

Please see INTRODUCTION of the BAY 12394 (PATENT-1) protocol.

In addition, the following aspects should be considered with respect to the long-term extension trial:

Based on the currently available scientific evidence, a large proportion of Pulmonary Artery Hypertension (PAH) patients cannot be cured. Therefore, it can be assumed that their disease will progress over the years, requiring a long-term medical treatment to maintain their quality of life and to increase their life expectancy.

Although the experiences with BAY 63-2521 with respect to the treatment of PAH are limited, in the light of the severity of the underlying disease it is justified to offer all patients who participated in the PATENT-1 trial a long-term treatment with BAY 63-2521 (until commercially available).

In this context, it should be highlighted that BAY 63-2521 revealed a positive benefit-risk ratio in the trials conducted in Pulmonary Hypertension (PH) patients to date (trials # 11874 and # 12166), allowing continuation of the development program. Moreover, in a first interim analysis of the extension phase of trial # 12166 (includes 21 patients with a BAY 63-2521 treatment up to one year) the improvements in walking distance observed within the first 12 weeks of treatment were sustained without any significant safety concerns.

For further information refer to the Investigator Brochure. The Investigator's Brochure will be updated at regular intervals during the conduct of the trial. New versions of the Investigator's Brochure will be made available to the investigators without delay

## 2. STUDY OBJECTIVES

To assess the long-term safety and tolerability of BAY 63-2521 in treatment naive patients and patients pretreated with an Endothelin Receptor Antagonist or a Prostacycline Analogue with symptomatic Pulmonary Arterial Hypertension (PAH).

The trial provides patients, who have completed 12 weeks of BAY 63-2521 double blind treatment (PATENT-1 trial, #12934), the option of long-term treatment with BAY 63-2521.

Efficacy assessments are included to provide an indication of maintenance of efficacy with long-term treatment.

## 4. INVESTIGATIONAL PLAN

### 4.1 Study Design and Plan

Multicentre, multinational, open label one arm study in patients with symptomatic PAH.

#### Study Phases:

- Treatment Phase:
  - Titration Phase: 8 weeks
  - Main-Study Phase: Duration until BAY 63-2521 receives official approval and will be commercially available
- Safety Follow Up Phase: 30 days

BAY 63-2521 will be administered orally as a tablet in doses of 0.5 mg, 1.0 mg, 1.5 mg, 2.0 mg, and 2.5 mg tid.

#### Titration Phase (8 weeks):

##### General aspects:

During the first eight weeks of the trial, patients from the Placebo Arm and from the BAY 63-2521 1.5 mg Dose Arm (applies only to patients who reached the 1.5 mg tid level) of PATENT-1 trial will be up-titrated, if tolerated, up to 2.5 mg BAY 63-2521 tid according to an individual dose titration scheme.

To maintain the blinding of PATENT-1, the PATENT-2 study medication (BAY 63-2521) is blinded with respect to the dose during the Titration Phase and investigators will not know at which dose level a certain patient enters the PATENT-2 trial.

Patients from the BAY 63-2521 Individual Dose Titration Arm and the BAY 63-2521 1.5 mg Dose Arm will enter the extension trial on the same dose level

which they have received on the last day of PATENT-1, while patients from the Placebo Arm will start at Visit 1 with a BAY 63-2521 dose of 1.0 mg tid.

To allow a blinded individual dose titration, the titration will be performed with the aid of an IVR-System. At each Titration Visit (with the exception of Visit 1) the investigator needs to decide, based on the patient's systolic blood pressure, if the study medication dose should be modified. The respective decision (increase, maintain or decrease dose) must be entered in the IVR-System that will automatically allocate the right dose in accordance with the respective titration scheme. Afterwards, the investigator will be informed by the system, which of the blinded medication bottles (blinded with respect to the dose) needs to be handed over for the next titration period (starts always with the morning dose).

Independently from the patient's allocation to a specific treatment arm in PATENT-1, the investigators will apply the following blood pressure based titration rules for their dose decision in PATENT-2:

The individual study medication dose of the next titration step will be determined every 2 weeks according to the peripheral SBP measured at trough before intake of the morning dose under consideration of the following algorithm (= individual dose titration scheme):

- If trough SBP  $\geq 95$  mmHg, increase dose (+0.5 mg tid).
- If trough SBP 90 - 94 mmHg, maintain dose.
- If trough SBP  $< 90$  mmHg without symptoms of hypotension, reduce dose (-0.5 mg tid).
- If any SBP  $< 90$  mmHg with clinical symptoms of hypotension such as dizziness or presyncope, stop study treatment; restart after 24 hours with reduced dose (-0.5 mg tid).

In general, if the investigator requests an increase or decrease of study medication dose via the IVR-System, the subsequent dose modification will not exceed plus/minus 0.5 mg study medication.

[figure not shown]
Although the individual dose titration scheme is solely based on the patient's systolic blood pressure, investigators are obliged to consider in addition the patient's well being. Therefore, it is allowed in case of study medication side effects, to suspend a foreseen up-titration step and to maintain the dose.

To request an increase of study medication dose is only possible at the planned study visits Visit 2, Visit 3 and Visit 4.

The Titration Phase ends at day 56 (Visit 5). At this visit the actual dose of the patients will be unblinded by the IVR-System.

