#### 4.6.3 Assessment Periods

##### Visit 1 at Day 0

Patients who finalized at Visit 6 the PATENT-1 trial and underwent invasive hemodynamic measurements may remain in the clinic until the next day (optional hospital stay).

At the day after finalization of PATENT-1 trial (= Visit 1 of PATENT -2), patients who fulfill the in/exclusion criteria and signed the informed consent form will be included into PATENT -2.

**Please Note:** it is not permitted to include a patient into the extension study on the same day of V6 of PATENT -1 (applies even if Visit 6 investigations were performed at two consecutive days).

On Visit 1 prior to first administration of PATENT-2 study medication, blood pressure and heart rate will be measured.

Subsequently, the patients will be allocated via the IVR-System to their individual BAY 63-2521 starting dose. In this context, the IVR-System will consider the patient's treatment arm allocation from the PATENT-1 trial (for further details refer to Section 4.1).

Two to three hours after the first intake of study medication, blood pressure and heart rate measurement will be repeated (for further details about the order of the procedures and the temporal relationship refer to Section 10.1).

Between six to eight hours after first study medication intake, the patients should take the second dose of study medication (second measurement cycle). One to zero hours before intake of second dose of study medication, blood pressure and heart rate will be measured, pharmacokinetic blood samples will be collected and a 12-lead electrocardiogram will be recorded. 2-3 hours after intake of second dose of study medication the blood pressure and heart rate should be measured (for further details about the order of the procedures and the temporal relationship refer to Section 10.1).

In addition to the measurements related to the measurement cycles, Adverse Events will be questioned and documented. Adverse events that occur before intake of first dose of PATENT-2 medication will be allocated to PATENT-1.

The study medication should be taken six to eight hours apart. If during the profile visit the systolic blood pressure falls below 90 mmHg with clinical symptoms of hypotension such as dizziness or presyncope, the study medication should be reduced by 0.5 mg tid or if deemed necessary interrupted (see section 4.1).

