### **Visit 2 at Day 14 / Visit 3 at Day 28 / Visit 4 at Day 42a**

adeviations from the scheduled visits of  $\pm 2$  days are permissible

Patients will return to hospital for an ambulatory assessment every 2 weeks without taking their morning dose of study medication. Before the dose of the study medication will be adjusted according to the titration scheme (refer to Section 4.1), blood pressure and heart rate will be measured, blood samples for clinical chemistry, hematology, coagulation parameters, NT-pro BNP will be collected, and a 12-lead electrocardiogram will be recorded.

Subsequently, based on the patient's SBP at trough, an individual decision with respect to a dose modification will be made (for further details refer to Section 4.1). The respective decision will be entered into the IVR-System. Afterwards, under consideration of the IVR-System's reply, the study medication for the next 2 weeks will be dispensed to the patients.

Two to three hours after intake of the morning dose of study medication, blood pressure and heart rate measurement will be repeated (for further details about the order of the procedures and the temporal relationship refer to Section 10.1).

Four to five hours after the intake of the morning dose of study medication 6MWD Test and an evaluation of Borg CR 10 Scale or Modified Borg Dyspnoea Scale (if

applicable) will be performed (for further details about the order of the procedures and the temporal relationship refer to Section 10.1).

In case that the SBP drops after intake of the morning dose below 90 mmHg with clinical symptoms of hypotension such as dizziness or presyncope, the study medication should be reduced by 0.5 mg tid or if deemed necessary interrupted for safety reasons (see section 4.1).

In addition to the measurements related to the cycle of measurements, the patient's concomitant medication will be updated, healthcare resource information will be collected, WHO functional class will be assessed, smoking status and Events of Special Interest as well as Adverse Events will be questioned and documented in the CRF.

The patients will be asked to return all unused study medication and the patient diary from the former visit for a compliance check.

Note: All blood pressure, heart rate measurements and ECGs should be performed in supine position at rest (for more details refer to Section 4.6.4).

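### For symptomatic SBP below 90 mmHg during titration, Protocol Section 4.1 directs a stop with a 24-hour pause, while the visit texts make the pause optional; the passages must be reconciled

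*Protocol*

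**What the plan says.** Protocol Section 4.1 (Titration Phase, general aspects) gives four blood-pressure rules, introduced with "the investigators will apply the following blood pressure based titration rules for their dose decision in PATENT-2". The first three concern SBP at trough. The fourth drops that restriction: it covers any SBP below 90 mmHg accompanied by symptoms of hypotension, and its action is "stop study treatment; restart after 24 hours with reduced dose (-0.5 mg tid".

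Section 4.6.3 returns to the same finding in the visit descriptions.

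- Visit 1: the trigger is "If during the profile visit the systolic blood pressure falls below 90 mmHg with clinical symptoms of hypotension" and the action is "the study medication should be reduced by 0.5 mg tid or if deemed necessary interrupted (see section 4.1".
- Visits 2 to 4: the trigger is "In case that the SBP drops after intake of the morning dose below 90 mmHg with clinical symptoms of hypotension" and the action is "the study medication should be reduced by 0.5 mg tid or if deemed necessary interrupted for safety reasons (see section 4.1".

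The action wording used for Visits 2 to 4 recurs at Visit 5, Visit 6 and Visits 7 to n.

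Two other places touch on the matter. The General Note at the end of Section 4.1 permits stops and safety reductions at any time. Section 4.3 leaves restart after a short interruption in titration to the investigator.

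**The concern.** The titration rules are written as directives and the visit texts as a choice. An investigator whose patient becomes dizzy with an SBP below 90 mmHg after a dose at Visit 2 can read Section 4.1 and stop treatment for 24 hours, or read Section 4.6.3 and only reduce the dose. Each has protocol text behind it.

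At stake is consistent handling of a safety event in a study whose objective is long-term safety and tolerability. Symptomatic hypotension is the protocol's own example of a safety reason for stopping or reducing. It is also unclear how to classify deviations: a reduction without a pause breaks Section 4.1 and complies with Section 4.6.3.

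**Working it through.** The protocol states no figure to reproduce here. The check is a comparison of the texts, followed by two small counts.

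**1. The texts side by side**

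| Place | Trigger | Reduction | Pause | Restart |
|---|---|---|---|---|
| Section 4.1, fourth rule | Any SBP below 90 mmHg with symptoms | 0.5 mg tid | Directed | After 24 hours |
| Section 4.6.3, Visit 1 | SBP below 90 mmHg with symptoms during the visit | 0.5 mg tid | At discretion | Not stated; points to 4.1 |
| Section 4.6.3, Visits 2 to 4 | SBP below 90 mmHg with symptoms after the morning dose | 0.5 mg tid | At discretion | Not stated; points to 4.1 |

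The threshold, the example symptoms and the size of the reduction match. Only the status of the pause differs. At Visits 2 to 4 the visit sentence covers post-dose drops only, so a symptomatic trough reading there falls under Section 4.1 alone.

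**2. Does any other text settle it?**

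- The cross-reference to Section 4.1 can supply the 24 hours once a site decides to interrupt. It does not say whether the site must: if Section 4.1 governs, the discretionary clause has no function; if the visit text governs, the stop in Section 4.1 is not a rule.
- The General Note in Section 4.1 allows both actions and requires neither.
- The well-being clause in Section 4.1 spells out only that an up-titration step may be withheld. It does not waive a stop.
- Section 4.3 gives discretion over restarting after a short interruption. That does not decide whether to interrupt, and it sits uneasily with a fixed restart after 24 hours.
- SAP Section 3 says the dose was decreased when SBP was below 90 mmHg. It does not distinguish by symptoms and mentions no pause.

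None of these resolves the difference.

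**3. Doses affected per event**

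Section 4.3 equates 3 days with 9 missed doses, so 9 / 3 = 3 doses per day.

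- Section 4.1: 24 h x 3 doses per 24 h = about 3 doses not taken, depending on timing.
- Reduction alone under Section 4.6.3: 0 doses missed.
- Interruption chosen under Section 4.6.3: up to the same 3 if the 24 hours are borrowed from Section 4.1.

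The divergence per event is therefore 0 to about 3 doses, and 3 is the maximum.

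**4. Scheduled readings under both texts, per patient**

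The inputs are Section 4.6.3 and the Visit Details in Appendix 10.1.

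- Visit 1, after the first dose: 2 to 3 hours after dose 1, before dose 2, and after dose 2 ("2-3 hours after intake of second dose of study medication the blood pressure and heart rate should be measured") = 3.
- Visits 2, 3 and 4: one post-dose reading each ("Two to three hours after intake of the morning dose of study medication, blood pressure and heart rate measurement will be repeated") = 3.
- Total: 3 + 3 = 6.

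The count depends on scope. Leaving out Visit 1 gives 6 - 3 = 3. Adding the post-dose reading at Visit 5 gives 6 + 1 = 7. These are occasions on which the trigger could be met, not expected events.

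**The case against.** The strongest defence is that Section 4.1 is the reference text. Both visit sentences point to it, as do Protocol Section 4.5.5 and SAP Section 3, so the visit wording can be read as shorthand for the full rule. This softens the conflict. It does not remove it, because no clause gives Section 4.1 precedence and the shorthand states a different action.

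A second argument is that the Section 4.1 rules serve the two-weekly dose decision at trough, from which Visit 1 is exempt. The fourth rule, however, is not limited to trough and is not tied to that decision, and the Visit 1 text itself refers to Section 4.1. Including Visit 1 remains an inference, which is why the count of 6 carries a lower figure of 3.

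Third, Visit 5 could be grouped with Visits 2 to 4, since its description says the dose is adjusted under the titration scheme. Against that, Section 4.1 ends titration and begins the Main-Study Phase at Visit 5, after which the scheme is one factor among several. The conflict is therefore weaker from Visit 5 on, and including Visit 5 would add one reading.

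Finally, the effect on the results is small. This stands: all analyses are descriptive (Protocol Section 6.1), no treated subject is excluded (SAP Section 4.6), and the exposure and titration summaries in SAP Section 6.1 would still describe what was taken. Protocol Section 5.2 already requires deviations to be explained and documented, but that does not help when the protocol leaves open what the deviation is.

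**Conclusion.** The contradiction is real and limited to one point: whether the pause is mandatory. It is direct at Visit 1 and Visits 2 to 4, and weaker at Visit 5, Visit 6 and Visits 7 to n. It should be corrected because it concerns a safety rule in a safety study.

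The size is at most about 3 doses per event, with 6 scheduled readings per patient exposed to both texts (3 to 7 depending on scope). No total effect can be estimated, because the documents give no frequency for the event; it is probably small. No compliance percentage is derived, because the documents do not say whether a stop directed by the protocol counts as planned dosing.

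The conclusion assumes that the fourth rule in Section 4.1 means what it says in covering any SBP reading. It rests on text alone: a figure following the titration rules in Section 4.1 could not be read. No view is taken on which action is clinically right.

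**What to change.** The sponsor's clinical team should reconcile the passages. Section 4.1 should carry one instruction for this trigger and say:

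- whether the pause is mandatory or discretionary;
- whether post-dose readings and the Main-Study Phase are handled differently;
- how the restart relates to the investigator's discretion in Section 4.3.

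The descriptions of Visits 1 to n in Section 4.6.3 should then refer to that instruction without restating a different action.

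If treatment is ongoing, the cost is a protocol wording change and a clarification to sites. Conduct may already be complete: the SAP for the final analysis is dated 25 Jul 2019 and describes titration in the past tense. In that case a short statement in the report is enough, saying which text was used to classify deviations and dose changes. No new data are needed.

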**Patients from the PATENT-1 Placebo Arm:**

For patients from the PATENT-1 Placebo Arm the starting dose will be 1 mg BAY 63-2521 tid. The individual BAY 63-2521 dose will be titrated every 2 weeks according to the peripheral SBP measured at trough before intake of the next morning dose. At the end of the Titration Phase (Visit 5) patients will have reached BAY 63-2521 doses between 0.5 mg tid and 2.5 mg tid.

Titration phase the same titration rules as for the PATENT-1 placebo patients, the individual dose cannot be increased above the dose received at last day of PATENT-1. If the investigator requests a dose increase above that level via the IVR-System, the patient will undergo a sham titration. Nevertheless, in case that the investigator requests a dose decrease (eg for safety reason), dose modifications are possible, but without a subsequent re-increase before Visit 5.

**Main-Study Phase (Duration until BAY 63-2521 receives official approval and will be commercially available):**

From Visit 5 on (begin of the Main-Study Phase) investigators are allowed to modify the BAY 63-2521 dose in a dose range between 0.5 mg tid and 2.5 mg tid according to the patient's need. In contrast to the Titration Phase, patients may be up-titrated between regular scheduled visits. In this context, investigators have to consider the patient's blood pressure (refer to the individual dose titration scheme), potential BAY 63-2521 side effects and the progression of the underlying Pulmonary Hypertension.

**Safety Follow Up Phase (30days)**

For all patients stopping study treatment at any time a Safety Follow Up Visit 30 days after stop of study medication intake should be performed.

**General Note:** Stop of study medication and dose reductions for safety reasons (eg patient suffers from severe symptomatic hypotension) are allowed at any point in time during the Titration and the Main-Study Phase. In case of intended dose reductions the investigator will contact the IVR-System, which can be done independently from any planned study visit, and request a dose reduction (- 0.5 mg study medication).

## **4.2 Selection of Study Population**

### **4.2.1 Inclusion Criteria**

- Patients who have completed 12 weeks of treatment in the double blind trial PATENT-1.
- Patients must have given their written informed consent to participate in the study after having received adequate previous information and prior to any study-specific procedures.

### **4.2.2 Exclusion Criteria**

- Patient's participating in another clinical trial
- Patients who have an ongoing serious adverse event from PATENT-1 that is assessed as related to BAY 63-2521 are not allowed to participate in the extension trial.
- Pregnant women (i.e. positive serum  $\beta$ -human-chorionic-gonadotropin test or other signs of pregnancy) or breast feeding women, or women with childbearing potential not using a combination of safe contraception methods.
- Patients with a medical disorder, condition, or history of such that would impair the patient's ability to participate or complete this study in the opinion of the investigator or the sponsor.
- Pertinent non compliance with the conditions for the trial or instructions by the investigator during PATENT-1 participation.
- Patients with hypersensitivity to the investigational drug or inactive constituents.

